4.2 Rationale for the Proposed Study

In this study, the impact of HI on the PK of single dose soticlestat [REDACTED]. After entering the body, drugs are eliminated by excretion and/or metabolism. Although elimination can occur through a variety of routes, most drugs are cleared by metabolism in the liver and/or small intestine and/or by elimination of unchanged drug by the kidney. Liver disease is associated with several pathophysiologic changes that may alter the PK of a drug. These include alterations in hepatic blood flow, changes in liver enzyme activity, decreased binding of drug to plasma proteins, and impaired biliary excretion [2, 3]. Accordingly, current United States (US) FDA guidance recommends a PK study in patients with impaired hepatic function if hepatic metabolism and/or excretion accounts for a substantial portion ($\geq 20\%$ of the absorbed drug) of the elimination of a parent drug or active metabolite [4].

The magnitude of the effect of mild, moderate, or severe HI on the PK of soticlestat was assessed based on model-based simulations of HI effect using in vitro enzyme phenotyping data and data from the human ADME study. The simulations suggested that in participants with mild, moderate, or severe HI, soticlestat AUC_{∞} is expected to be 1%, 23%, and 33% higher, respectively, than healthy participants with normal hepatic function; soticlestat C_{max} is expected to be 0%, 6%, and 7% higher, respectively, compared with healthy participants with normal hepatic function.

Based on model-based simulations, this study first evaluated the PK in participants with moderate HI (n=8) and healthy matched participants with normal hepatic function (n=12) and an interim PK analysis was conducted. The interim analysis indicated higher impact of moderate HI on soticlestat PK than the model predicted. For participants with moderate HI, soticlestat PK exposure increased to 214.93%, 316.47%, and 299.38% for C_{max} , AUC_{last} , and AUC_{∞} , respectively, when compared to the respective PK exposure in matched participants with normal hepatic function. As a result, this study will further evaluate the impact of mild HI on the PK of soticlestat. In addition, the Sponsor decides not to dose participants with severe HI. Soticlestat will not be recommended to use in subjects with severe HI.

4.3 Benefit/Risk Profile

The single dose of 300 mg soticlestat has been selected for this study as it is the recommended phase 3 dose [1]. In addition, doses up to 1350 mg were administered in healthy participants and were found to be safe and well tolerated.

The inclusion and exclusion criteria, screening, and safety monitoring practices employed by this protocol (ie, 12-lead ECG, vital signs, clinical laboratory tests, AE questioning, C-SSRS, and physical examinations) are adequate to protect the participant's safety and should detect all TEAEs.

There will be no direct health benefit for study participants from receipt of the study drugs. An indirect health benefit to the healthy participants enrolled in this study is the free medical tests received at screening and during the study.

5.0 STUDY OBJECTIVES AND ENDPOINTS

5.1 Hypothesis

Not applicable.

5.2 Study Objectives

5.2.1 Study Primary Objective

- To characterize the plasma PK of soticlestat following a single oral dose in participants with moderate or mild HI compared to matched healthy participants with normal hepatic function.

5.2.2 Study Secondary Objective

- To evaluate the safety and tolerability of soticlestat following a single oral dose in participants with moderate or mild HI as well as matched healthy participants with normal hepatic function.

5.3 Endpoints

5.3.1 Primary Endpoints

The following PK parameters in plasma will be analyzed for soticlestat:

- C_{max}
- AUC_{∞}
- AUC_{last}

5.3.2 Secondary Endpoints

- Incidence of TEAEs
- Incidence of clinically significant abnormal values for laboratory evaluations, vital signs, ECG parameters, and C-SSRS

6.0 STUDY DESIGN AND DESCRIPTION

6.1 Study Design

This is a phase 1, open-label, study of oral soticlestat designed to assess the PK of single dose soticlestat [REDACTED] in participants with moderate or mild HI compared to matched healthy participants with normal hepatic function. At least 12 healthy participants (up to 24 participants) with normal hepatic function will be recruited to match the group mean of moderate and mild HI arms by age (mean \pm 10 years), sex (\pm 2 per sex), and BMI (mean \pm 10%). Eight (8) participants will also be enrolled in each HI arm of the study according to the following criteria:

- Arm 1: (N = 8): Moderate HI (Child-Pugh Class B [Score: ≥ 7 and ≤ 9]), 300 mg single dose
- Arm 2: (N = 8): Mild HI (Child-Pugh Class A [Score: ≥ 5 and ≤ 6]), 300 mg single dose
- Arm 3: (N = 12 - 24): Normal hepatic function, 300 mg single dose

The study will consist of a 28-day screening period (prior to dosing) and a 7-day confinement period (Day -1 to Day 7).

Two hepatic function assessments are required prior to Day 1 dosing for participants with HI. These 2 assessments should be obtained during the screening period and at least 48 hours apart. In the case, where a participant has an available historical Child-Pugh assessment score within 3 months prior to screening, 1 assessment can be conducted during the screening period. If the Child-Pugh scores from these 2 assessments indicate the same liver function category for the participant (ie, normal hepatic function, moderate HI, or mild HI), soticlestat can be administered as scheduled. If the results of the 2 assessments indicate different liver function categories, a third assessment must be conducted at least 24 hours after the second assessment. If the results of the 2 most recent assessments (the second and third) are in agreement with regard to the participant's liver function category, the participant may be enrolled and should receive the Day 1 dose within 48 hours of the third assessment. If the second and third measurements differ, the participant will not be eligible for the study.

The moderate HI arm (ie, Arm 1) will be conducted first, followed by 12 participants in the matched normal hepatic function arm (Arm 3). After all participants in moderate HI arm and the matching 12 participants in the matched normal hepatic function arm have completed the treatment period, an informal interim PK data analysis is planned and may additionally leverage historical control PK data in healthy participants to gain an initial estimate of the effect of moderate HI on the PK of soticlestat [REDACTED].

Following completion of enrolment of the mild HI arm, and in the instance any of the previously enrolled healthy participants cannot be used for matching purposes, up to an additional 12 participants may be enrolled for the matched normal hepatic function group (Arm 3) to ensure a minimum of 12 participants with normal hepatic function and matching the mean of the mild HI arm by age (mean \pm 10 years), sex (\pm 2 per sex), and body mass index (BMI, mean \pm 10%) are enrolled.

Participants will receive a single oral dose of 300 mg soticlestat as three 100 mg T4 tablets on Day 1 with approximately 240 mL water under fasting conditions. PK samples will be collected from Days 1 to 7, at predetermined time points (Section 3.0), to characterize the PK of soticlestat [REDACTED] in participants with moderate or mild HI compared to matched healthy participants with normal hepatic function (Section 3.0).

Participants will remain in the clinic throughout the study. Participants will be discharged from the clinic on Day 7 after the last PK sample collection and study procedures are completed. A safety follow-up contact of all participants (including those who terminate the study early) will occur 14 \pm 2 days after the soticlestat dose to determine if any AEs have occurred since the CRU discharge.

6.2 Dose Escalation

Not applicable.

6.3 Stopping Rules

Not applicable.

6.4 Rationale for Study Design, Dose, and Endpoints

6.4.1 Rationale of Study Design

After entering the body, drugs are eliminated by excretion and/or metabolism. Although elimination can occur through a variety of routes, most drugs are cleared by metabolism in the liver and/or small intestine and/or by elimination of unchanged drug by the kidneys. Liver disease is associated with several pathophysiologic changes that may alter the PK of a drug. These include alterations in hepatic blood flow, changes in liver enzyme activity, decreased binding of drug to plasma proteins, and impaired biliary excretion [2, 3]. Accordingly the current United States (US) Food and Drug Administration (FDA) guidance recommends a PK study in patients with impaired hepatic function if hepatic metabolism and/or excretion accounts for a substantial portion (ie, $\geq 20\%$ of the absorbed drug) of the elimination of a parent drug or active metabolite [4]. Urinary excretion is the major route for soticlestat elimination with 95% of the dose excreted in urine; however, urinary excretion of the parent drug is low (< 1% of the dose) indicating that metabolism is the near exclusive clearance pathway of soticlestat. TAK-935-G excreted in urine contributed to 86% of the dose suggesting that soticlestat was predominantly cleared by direct glucuronidation, thus the potential implications of HI on soticlestat's hepatic metabolism, should be evaluated.

This study will investigate the impact of impaired hepatic function on the plasma PK of soticlestat [REDACTED] and safety compared to matched healthy participants with normal hepatic function in order to provide dosing recommendations to clinicians for future treatments of soticlestat to patients with varying degrees of HI. An informal interim PK data analysis was performed following soticlestat administration in participants with moderate HI ($n=8$) and healthy matched participants with normal hepatic function, which has demonstrated higher than expected soticlestat exposure in participants with moderated HI than in healthy matched participants with normal hepatic function. The Sponsor has decided not to recommend soticlestat dosing in patients with severe HI, therefore participants with severe HI will not be enrolled in the current study. Instead, this study will enroll an arm of participants with mild HI in order to further investigate the impact of HI on soticlestat PK. Due to the variability of soticlestat PK and easier accessibility of healthy participants in comparison to participants with HI, an increased number of healthy participants will be enrolled.

The Child-Pugh classification will be used to categorize HI due to its widespread use and acceptance by regulatory agencies (including the FDA). It has been shown to correlate with hepatic (ie, metabolic) clearance for several compounds [4]. In the current study, participants with chronic, stable HI with features of cirrhosis due to any etiology will be enrolled using the

Child-Pugh scale. The scale employs five clinical measures of liver disease listed in [Table 6.a](#). Each assessment is scored 1 - 3, with 3 indicating most severe derangement. Participants' scores of 5 to 6, 7 to 9, and 10 to 15 on this scale are classified as having mild, moderate, and severe HI, respectively.

Table 6.a Derivation of Child-Pugh Classification Score¹

Parameter	1 point	2 points	3 points
Serum albumin (g/dL)	>3.5	2.8 to 3.5	<2.8
Total serum bilirubin (mg/dL)	<2.0	2.0 to 3.0	>3.0
Prothrombin time (PT) (second prolonged) or International normalized ratio (INR) (ratio)	<4 <1.70	4 to 6 1.70 to 2.30	>6 >2.30
Ascites	Absent	Slight	Moderate or participants on medication to control ascites
Hepatic encephalopathy grade	None	Grade 1 or 2	Grade 3 or 4 or participant receiving medication(s) to prevent encephalopathy

¹ Adapted from U.S. Department of Health and Human Services. Guidance for Industry. Pharmacokinetics in Patients with Impaired Hepatic Function: Study Design, Data Analysis, and Impact on Dosing and Labeling (2003) [\[4\]](#).

Table 6.b Determination of Encephalopathy Grade¹

Encephalopathy Grade	Definition
0	Normal consciousness, personality, neurological exam
1	Restless, sleep disturbed, irritable/agitated, tremor, impaired handwriting
2	Lethargic, time-disoriented, inappropriate, asterixis, ataxia
3	Somnolent, stuporous, place-disoriented, hyperactive reflexes, rigidity
4	Unrousable coma, no personality/behavior, decerebrate

¹ Adapted from U.S. Department of Health and Human Services. Guidance for Industry. Pharmacokinetics in Patients with Impaired Hepatic Function: Study Design, Data Analysis, and Impact on Dosing and Labeling (2003) [\[4\]](#).

6.4.2 Rationale for Dose

T4 tablets are immediate release tablets of 100 mg strength that will be utilized for phase 3 clinical studies and will be used in this study. The model simulation (SimCYP[®]) predicted increase in soticlestat exposure in participants with moderate or mild HI is within two-fold, therefore the dose of soticlestat selected for the HI study is 300 mg, the recommended phase 3 dose. The 300 mg dose is approximately 22% of the highest single dose of 1350 mg evaluated in healthy participants, and soticlestat exposure at 1350 mg was > 4-fold the exposure at 300 mg. In clinical studies, soticlestat administered as a single dose of up to 1350 mg was safe and well tolerated. As metabolism is the near exclusive clearance pathway of soticlestat in humans, the effect of moderate or mild HI on the exposure to soticlestat [REDACTED] will be characterized in this study

to establish scientifically guided dosing recommendations in these special patient populations. The PK of soticlestat [REDACTED] following oral administration of soticlestat in participants with moderate or mild HI using Child-Pugh scores will be compared to matched healthy participants with normal hepatic function.

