The PK profile following single-dose and multiple-dose administration were further characterized in healthy Japanese participants (Study TAK-935-1004). Soticlestat was rapidly absorbed after administration, with t_{max} of 0.5 to 0.75 hours. Soticlestat $t_{1/2z}$ values ranged from 5.075 to 8.695 hours after a single-dose and from 2.620 to 3.630 hours after multiple doses with up-titration. PK exposure to soticlestat increased in a greater than dose-proportional manner in the dose ranges from 200 to 1200 mg single dose and 100 to 300 mg BID. Accumulation of 100 BID dosing was minimal for C_{max} and AUC of soticlestat with accumulation ratios less than 1.06 at steady state. [REDACTED]

[REDACTED]

[REDACTED]

[REDACTED]

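### Does the two-fold prediction in the dose rationale (Protocol 6.4.2) call for a change, now that Protocol 4.2 reports observed ratios above it?

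*Protocol*

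**What the plan says.** Protocol 6.4.2 (Rationale for Dose) reasons from a simulation: "predicted increase in soticlestat exposure in participants with moderate or mild HI is within two-fold, therefore the dose of soticlestat selected" is 300 mg, which the same sentence identifies as the recommended phase 3 dose. It adds that 300 mg is about 22% of the highest single dose given to healthy participants, and that "soticlestat exposure at 1350 mg was > 4-fold the exposure at 300 mg".

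Protocol 4.2 gives the predictions. For mild, moderate and severe HI, AUC∞ "is expected to be 1%, 23%, and 33% higher, respectively", and the corresponding Cmax increases are 0%, 6% and 7%. It then reports the completed interim comparison of 8 participants with moderate HI and 12 matched participants: "soticlestat PK exposure increased to 214.93%, 316.47%, and 299.38" percent of the matched normal value for Cmax, AUClast and AUC∞. It draws the conclusion itself: "The interim analysis indicated higher impact of moderate HI on soticlestat PK than the model predicted". Section 6.4.1, directly before the dose rationale, refers to the interim analysis, "which has demonstrated higher than expected soticlestat exposure in participants with moderated HI".

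Protocol 4.3 gives the recommended phase 3 dose as the reason for 300 mg and adds that "doses up to 1350 mg were administered in healthy participants and were found to be safe and well tolerated". It does not use the two-fold prediction. Section 6.5 says that the dose may not be modified in any arm.

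**The concern.** The word linking prediction to dose in 6.4.2 makes the prediction a premise, not background. The same protocol version reports that exposure in moderate HI went past two-fold on all three primary PK parameters. The section was edited in this amendment, since it now names mild HI, yet it does not mention the interim result. Neither does the benefit/risk text in 4.3.

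If this mattered, it would matter in two ways. Someone who read 6.4.2 alone would believe that exposure in moderate HI stays within two-fold. And the mild arm, still to be enrolled, would rest partly on a model that the protocol says under-predicted in the only impaired group observed so far.

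**Working it through.** **Inputs.** Predicted increases and observed percentages: Protocol 4.2. Two-fold statement, 22% and more than 4-fold: Protocol 6.4.2. The observed percentages are read as ratios to the matched normal group, which is the plain sense of an increase *to* a percentage.

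**1. Reproduce the figures in 6.4.2.**
- Predicted ratio = 1 + stated increase. Mild: AUC∞ 1.01, Cmax 1.00. Moderate: AUC∞ 1.23, Cmax 1.06. All are below 2, so the sentence reports the prediction correctly.
- Dose fraction: 300/1350 = 22.2%, matching the stated 22%.

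**2. Compare the observed moderate-HI ratios with two-fold and with the prediction.**

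| Parameter | Observed | Observed / 2 | Observed / predicted |
|---|---|---|---|
| Cmax | 2.149 | 1.07 | 2.149/1.06 = 2.03 |
| AUClast | 3.165 | 1.58 | no prediction given |
| AUC∞ | 2.994 | 1.50 | 2.994/1.23 = 2.43 |

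All three point estimates exceed two-fold, by 7%, 58% and 50%. For moderate HI the premise did not hold.

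**3. Compare the observed ratios with the other exposure figure in 6.4.2.** The ratios of 2.15, 3.16 and 2.99 are all below 4. Dividing the stated lower bound by them gives 4/2.149 = 1.86, 4/3.165 = 1.26 and 4/2.994 = 1.34. These quotients should not be set against 4/2 = 2.0 as though the protocol claimed a margin of that size. It claims none, the 4-fold figure is an open lower bound, and 6.4.2 does not say whether it refers to Cmax or AUC. The dose ratio alone is 1350/300 = 4.5. Section 4.1.1.2 reports, in healthy Japanese participants, that "PK exposure to soticlestat increased in a greater than dose-proportional manner in the dose ranges from 200 to 1200 mg single dose"; that range stops short of 1350 mg.

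**4. Ask what a similar model error would mean for mild HI.** Assume that the whole moderate-HI under-prediction carries over. Then AUC∞ would be 1.01 × 2.43 = 2.46 and Cmax 1.00 × 2.03 = 2.03. Both would pass two-fold and stay below 4. This is an assumption; the documents hold no mild-HI data.

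**5. Check the precision of the observed ratios.** Section 4.2 gives no interval. If the between-participant CV is assumed to be 30% to 100%, with 8 against 12 participants and a common variance on the log scale, the 90% interval is ratio × exp(±t × s × √(1/8 + 1/12)), where s = √ln(1 + CV²) and t is the 95th percentile on 18 degrees of freedom. For Cmax it runs from 1.70–2.71 (CV 30%) to 1.11–4.15 (CV 100%). For AUClast it runs from 2.51–3.99 to 1.64–6.12. Steps 2 and 3 are therefore statements about point estimates only.

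**6. Look for anything that uses the two-fold figure.**
- Sample size (Protocol 11.3, SAP 4.0) is not based on power and takes no expected ratio.
- SAP 3.1 and 3.2 set no hypotheses or decision rules.
- The primary analysis (Protocol 11.1.3, SAP 6.8) estimates each ratio from the data with a 90% CI.
- SAP 6.10 repeats that the effect exceeded the prediction.

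The figure appears in the rationale text and nowhere in conduct or analysis.

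**The case for a change.** The best case for a change grants that the prediction is reported correctly and points to how it is used. A premise that the sponsor's own data did not bear out should not stand in the section that justifies the dose, least of all while an arm is still to be enrolled and the mild prediction comes from the same simulations. Disclosure elsewhere is what makes 6.4.2 out of step, and the repair costs a few sentences drawn from data already held.

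Part of this stands. Section 6.4.2 is out of date for moderate HI, and it does not say which of its supports it now relies on.

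The rest carries less weight. A reader who goes through the rationale in order meets the interim result in 4.2 and again in 6.4.1 before reaching 6.4.2. The recommended phase 3 dose is a separate stated basis in both 6.4.2 and 4.3, and the interim result does not bear on it. Appendix E lists 6.4.2 only under the replacement of severe by mild HI. Its entry for the added amendment rationale names only 4.2 and 6.4.1, where the result does appear, so the log does not show that 6.4.2 was meant to carry it. Interim confidence intervals in a dose rationale would be a preference: the SAP already provides 90% CIs in the final analysis. A rewording alone would also need IRB or IEC approval as a protocol change (Appendix A, item 6).

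**Conclusion.** The inconsistency is real but confined to wording, and correcting it would bring no gain to the trial. Section 6.4.2 cites a prediction that, on the interim point estimates, was exceeded in moderate HI by 7% (Cmax) to 58% (AUClast) relative to two-fold. Section 4.2 of the same document reports those estimates and says that the model under-predicted. The moderate arm has been dosed, no observation contradicts the mild prediction, and no endpoint, sample size, analysis or dosing instruction depends on the figure.

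This rests on three things. First, the reported percentages are ratios; if they were increments, the values would be 3.15, 4.16 and 3.99, and AUClast would pass 4. Second, the comparison with the 4-fold figure uses point estimates from 8 against 12 participants; under the CVs assumed above, the upper 90% limit for AUClast runs from 3.99 to 6.12. Third, the exposure measure behind the 4-fold figure is not stated. None of these alters how the trial is run or analysed.

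Sections 6.4.2 and 4.2 remain to be reconciled as a matter of record. That is a documentation note, and it implies no view on the dose.

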6.4.3 Rationale for Endpoints

6.4.3.1 Pharmacokinetic Endpoints

The PK endpoints are standard for this type of study.

6.4.3.2 Safety Endpoints

The key safety endpoints are typical for phase 1 studies and will be assessed through monitoring of AEs, vital signs, ECGs, laboratory assessments, C-SSRS, and physical examinations.

6.4.5 Critical Procedures Based on Study Objectives: Timing of Procedures

For this study, the critical component is the blood collection for plasma concentrations of soticlestat [REDACTED], and is to be collected within the sampling windows.

6.5 Study Design/Dosing/Procedures Modifications Permitted Within Protocol Parameters

The dose and administration of soticlestat for all participants with moderate HI, mild HI, and healthy participants with normal hepatic function (ie, Arms 1, 2, and 3) may not be modified.

After all participants in the moderate HI arm and 12 participants in the matched normal hepatic function arm have completed the treatment period, an informal interim PK data analysis is planned and may additionally leverage historical control PK data in healthy participants to gain an initial estimate of the effect of moderate HI on the PK of soticlestat [REDACTED]. Following completion of enrolment of the mild HI arm, and in the instance any of the previously enrolled healthy participants cannot be used for matching purposes, up to an additional 12 participants may be enrolled for the matched normal hepatic function group (Arm 3) to ensure a minimum of 12 participants with normal hepatic function and matching the mean of the mild HI arm by age (mean \pm 10 years), sex (\pm 2 per sex), and body mass index (BMI, mean \pm 10%) are enrolled.

If necessary, a participant may be discontinued for the reasons described in Section 7.5 and Section 7.6.

